Design:

This study is a prospective and single blinded randomized control trial. The inclusion or the exclusion criteria will be assessed by the same physician before the patients are invited to join the trial. After the selected patients have signed the informed consent sheets, they will be randomized into two groups (21 patients in each group), the radial shockwave therapy group (RSWT group), the botulinum toxin injection group, and the control group. The randomization will be generated by a computer program and the allocation will be done with concealed envelops. Both the patients and the examining physicians are blind to the allocation. Treatment will be performed by another independent physician.

Participants:

Totally, 42 patients will be recruited from the department of Physical Medicine and Rehabilitation of the Taipei MacKay Memorial Hospital. Eligible subjects should meet the following inclusion criteria: (1) aged between 18 ~ 80 years old; (2) at least 6 months since onset of last stroke; (3) having at least 1+ in modified Ashworth Scale (MAS) score at the spastic elbow; (4) most important of all, read and signed the inform concern of this study.

The exclusion criteria are the following: (1) patients with elbow contracture (MAS=4); (2) patient who had prior history of botulinum toxin, phenol, alcohol injections, intrathecal baclofen pump or rhizotomy in six months; (3) having evidence of cognitive deficit; (4) having local infection, severe inflammation or otherwise lesion that is not suggestive for ESWT; (5) patient with serious medical problems, as uncontrolled hypertension,

coagulopathy, recent severe hemorrhage, neoplasm, severe hepatic disease, epilepsy, cutaneous pathology, mental retardation.

During the study period, physical therapy including range of motion (ROM) exercises, stretching, and others remained unchanged. Also, the doses of medication which might affect spasticity were not changed.

Interventions:

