For each group, totally 3 section of therapy will be given in an interval of one week. The shock wave will be given by a two combined ESWT device from which 3000 impulses of shock waves with energy flux density of 1.5 bars and frequency of 5 Hz are delivered in the radial shock wave therapy group. For botulinum toxin group, botulinum toxin (dilution 500 U/2 mL in saline 0.9%) was administered. For the control group, a sham probe will be contacting the skin with the same therapeutic sound made. However, no energy will be delivered from the sham probe. The location of the applied therapy will be at biceps, flexor carpi radialis (FCR) and flexor carpi ulnaris (FCU) muscles.

Outcome measures:

The primary outcome of this study include, elbow and radio carpal joint range of motion (ROM), modified Ashworth scale (MAS), modified Tardieu scale (MTS), and Fugl-meyer assessment (FMA). The evaluation will be done before therapy sections, immediately, 1 month after, and 3 months after 3rd section of therapy. All examination will be done by the same examining physician who is blind to the allocation.

Modified Ashworth scale (MAS). The definition of the measured scales were as that proposed by Bohannon and Smith.³ Briefly, elbow joint range of motion will be performed manually. MAS is graded by the resistance felt during passive range of motion. However, for convenience in the statistical analysis, MAS 1+ was substituted by scale of 2, and 2, 3, and 4 were substituted by 3, 4, and 5, respectively.

Modified Tardieu scale (MTS). The definition of the measurement was as that proposed by Boyd and Graham (modified from Tardieu scale).^{4,5} In brief, the measurement of elbow and radio carpal range of motion will be performed at a slow and a fast velocity. The resulted joint angles at two speeds will be measured by goniometer. R1 angle is defined as angle of catch after a fast speed stretch and R2 angle is defined as angle measured during slow speed range of motion. The average of three testing will be used for analysis. The quality of muscle reaction during measurement will also be scaled.

Fugl-meyer assessment (FMA) The Fugl-Meyer assessment is designed to assess motor recovery following stroke. The maximum score of motor function of upper limbs were 66. It is a relatively simple assessment to administer and requires minimal training. The overall reliability for this instrument was high, as were the reliability measurements for the subsections of this assessment.

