Statistical analysis.

All statistic data will be analyzed by SPSS statistical software, version 20.0 (SPSS Inc., Chicago, USA). The homogeneity of patient demographic

characteristics in both comparative groups A and B were calculated with chi-square test for qualitative variables (gender, stroke subtype, affected site) and the ANOVA test for quantitative variables (age, weight, height, body mass index [BMI], time since onset of stroke). The differences between 3 groups were investigated using the repeated measures ANOVA followed by the Bonferroni post hoc tests. Statistical significance was set at $P<0.05$.

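### The repeated measures ANOVA gives the pre-treatment outcome value no covariate role; adjusting for it would make a named contrast more precise at almost no cost

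*Combined protocol and SAP*

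**What the plan says.** Under Outcome measures, each outcome is assessed once before treatment and three times after it: "The evaluation will be done before therapy sections, immediately, 1 month after, and 3 months after 3rd section of therapy". Range of motion, the modified Ashworth scale (MAS), the modified Tardieu scale (MTS) and the Fugl-Meyer assessment (FMA) are all called primary.

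Under Statistical analysis, the comparison of groups is one sentence: "The differences between 3 groups were investigated using the repeated measures ANOVA followed by the Bonferroni post hoc tests". It names no covariate. It does not say whether the pre-treatment visit is a level of the time factor, or whether the group effect or the group-by-time effect is the treatment test. It names no sphericity correction.

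The section's only other use of baseline data is a check of comparability between groups. The continuous variables there are tested by "the ANOVA test for quantitative variables (age, weight, height, body mass index [BMI], time since onset of stroke". No outcome is on that list.

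The trial is small: "Totally, 42 patients will be recruited from the department of Physical Medicine and Rehabilitation". The number of arms is unclear. The Design section says "they will be randomized into two groups (21 patients in each group" and then lists three groups, and the analysis sentence refers to three.

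**The concern.** The pre-treatment value of an outcome is usually the best single predictor of its later value. In a repeated measures ANOVA over all four visits it can enter only as one more level of time. The group-by-time contrast then rests on change from baseline, which subtracts the whole baseline value whatever its correlation with follow-up. Covariate adjustment subtracts only the predictive part, so for the same contrast it has the smaller variance whenever the correlation is below 1, before the small cost of estimating the slope.

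With 42 patients, perhaps 14 per arm, precision is scarce and the data needed are already being collected. What is at stake is power and the width of confidence intervals, not the validity of the comparison.

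**Working it through.** **Inputs from the documents.** Total 42 patients; one pre-treatment and three post-treatment visits; significance level 0.05. The 42 comes without power, effect size or SD. The only arithmetic behind it is 2 × 21 = 42, so there is no power figure to reproduce.

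**Assumptions, for illustration.** SD of 1 at every visit; both active arms differ from control by 0.8 SD, equally at each post-treatment visit; complete data; three arms of 42/3 = 14; the same correlation ρ between all visits unless stated.

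**Step 1: variance per patient for the same contrast.**
- One visit: change 2(1 − ρ); adjusted 1 − ρ²; ratio 2/(1 + ρ).
- Post-visit mean, with V = (1 + 2ρ)/3: change V + 1 − 2ρ; adjusted V − ρ²; ratio 4/(1 + 3ρ).

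| ρ | One visit: change | adjusted | ratio | Post mean: change | adjusted | ratio |
|---|---|---|---|---|---|---|
| 0.3 | 1.400 | 0.910 | 1.54 | 0.933 | 0.443 | 2.11 |
| 0.5 | 1.000 | 0.750 | 1.33 | 0.667 | 0.417 | 1.60 |
| 0.7 | 0.600 | 0.510 | 1.18 | 0.400 | 0.310 | 1.29 |
| 0.9 | 0.200 | 0.190 | 1.05 | 0.133 | 0.123 | 1.08 |

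**Step 2: cost of estimating the slope.** Residual degrees of freedom fall from 39 to 38, and the adjusted variance is inflated by about 1 + 1/37 = 1.027. For one visit, 2/(1 + ρ) = 1.027 gives break-even at ρ ≈ 0.947. For the post-visit mean, 4/(1 + 3ρ) = 1.027 gives ρ ≈ 0.965. The gain is therefore nil at about 0.95.

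**Step 3: power of the overall F test at 0.05.** S = 14 × [(0 − 0.533)² + 2 × (0.8 − 0.533)²] = 5.973, and the noncentrality is S divided by the variance. For the post-visit mean at ρ = 0.5, change gives 5.973/0.667 = 8.96 on (2, 39) df, or 73.4%. Adjusted gives 5.973/0.417 = 14.3 on (2, 38) df, or 91.3% (90.6% by simulation, which includes the slope cost).

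| ρ | One visit: change → adjusted | Post mean: change → adjusted |
|---|---|---|
| 0.3 | 41% → 58% | 58% → 89% |
| 0.5 | 55% → 67% | 73% → 91% |
| 0.7 | 78% → 84% | 92% → 97% |

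**Step 4: post-treatment visits more alike than baseline and follow-up.** With baseline-post 0.5 and post-post 0.8, V = 2.6/3 = 0.867. Change is 0.867 and adjusted is 0.617, a ratio of 1.41, and power for the post-visit mean goes from 61% to 76%. With 0.3 and 0.8 it goes from 45% to 66%.

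**Step 5: high correlation.** At ρ = 0.9 with a 0.5 SD effect, one visit goes only from 84.5% to 85.4%, and the post-visit mean from 95.9% to 96.7%. At ρ = 0.95 with a 0.3 SD effect, one visit is 70.4% unadjusted and 70.3% adjusted.

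**Step 6: other layouts at ρ = 0.5, 0.8 SD.** For a pairwise comparison at 0.05/3 with 14 per arm, one visit goes from 36% to 47% and the post-visit mean from 54% to 76%. For two arms of 21 at 0.05, the post-visit mean goes from 87% to 97%.

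**Step 7: the two tests the plan's sentence could mean.**
- *Group main effect over four visits.* A constant effect is averaged with a pre-treatment visit where it is zero: (0 + 1 + 1 + 1)/4 = 75%. Noncentrality is S × 0.75²/[(1 + 3ρ)/4], which gives power of 50% at ρ = 0.5 and 42% at ρ = 0.7.
- *Group-by-time.* The effect is not diluted. Noncentrality is S × 0.75/(1 − ρ), which gives 56% and 82%. These lie below the post-visit mean partly because the test spreads over 6 numerator df. That part of the gap comes from naming a focused contrast, not from adjustment.

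**Step 8: error rate of group-by-time without a correction.** In 20,000 simulated null trials, the uncorrected test rejects in 7.1% (correlations 0.5/0.8) and 8.0% (0.3/0.8). With Greenhouse-Geisser the rates are 4.9% and 5.0%.

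**The case against.** The strongest reply is that repeated measures ANOVA is a valid, familiar method that already uses the pre-treatment visit as a level of time. This stands: the issue is a choice between two valid analyses. A reader might infer that the plan discards the baseline or gives a biased comparison. The documents support neither. They are silent on whether baseline is a time level, and randomisation protects the contrast either way.

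A second reply is that the correlation may be high. Patients are at least six months from stroke, background therapy and medication are held constant, one examiner does all assessments, and Tardieu angles are averaged over three tests. All this makes a high ρ plausible for the angles and FMA, though no figure is given. At 0.9 the gain is about one percentage point, so it would be wrong to say that adjustment always helps.

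A third reply is that the largest gains belong to a post-visit mean that the plan never names. This also stands. A reader might conclude that a baseline-adjusted model beats the planned ANOVA whatever is tested. It does not:
- With a constant effect and correlations 0.5/0.8, the joint adjusted test over three visits has about 54% power, against 59% for corrected group-by-time. With equal correlations of 0.5 the order reverses, about 73% against 53%.
- If the effect exists only at the first post-treatment visit (ρ = 0.5), the adjusted mean has about 17% power, against 56% for group-by-time. The adjusted contrast at that visit has 67%.

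Finally, the 75% dilution applies only if the group main effect over four visits is the treatment test, which the plan does not say.

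**Conclusion.** The point holds as one of efficiency. For the same named contrast, whether one visit or the post-visit mean, adjusting for the pre-treatment value reduces variance relative to change from baseline. The reduction is substantial at low to moderate correlation, small at 0.9 and nil at about 0.95 with 42 patients. At ρ = 0.5 under the stated assumptions it is worth about 12 percentage points of power at one visit and 18 for the post-visit mean (15 if the post-treatment visits correlate at 0.8).

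The direction does not depend on the effect size or on whether there are two or three arms. The size depends on a correlation that the documents do not give. The advantage is not claimed for omnibus tests across visits, and no bias is alleged. For MAS the gain is only approximate and probably smaller: it is a recoded ordinal score ("for convenience in the statistical analysis, MAS 1+ was substituted by scale of 2"), and the entry criteria leave three possible elbow grades at baseline (1+, 2 and 3).

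**What to change.** Replace the analysis sentence with wording such as: *Each outcome analysed as a score or angle is modelled over the three post-treatment visits with group, visit, group-by-visit, the pre-treatment value of the same outcome, and that value by visit. The treatment test is [the average over the three post-treatment visits, or one named visit]. With three arms, pairwise comparisons are Bonferroni-adjusted.*

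The trialists should fill the bracket before any data are seen, because it settles whether the trial asks about a sustained effect or about a particular time. The average is a poor choice if the effect is expected to be short-lived. If there are two arms, no pairwise adjustment is needed; the number of arms has to be reconciled separately.

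If the repeated measures ANOVA is kept, state that group-by-time is the treatment test and apply a Greenhouse-Geisser correction.

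The cost is a change of wording, a different SPSS procedure and one residual degree of freedom (38 instead of 39 with three arms of 14). No new data or visits are needed. For MAS, report the result with the caveat that the model is approximate, as it already is for the planned ANOVA.

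### The only outcome analysis named, repeated measures ANOVA over four evaluations, conventionally discards all of a patient's data on an outcome if one visit is missing, and the plan has no rule that keeps the values already collected

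*Combined protocol and SAP*

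**What the plan says.** The Outcome measures section fixes the schedule: "The evaluation will be done before therapy sections, immediately, 1 month after, and 3 months after 3rd section of therapy". That is four evaluations: one before treatment and three after.

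The Statistical analysis section gives the software, "All statistic data will be analyzed by SPSS statistical software, version 20.0", and one method for outcomes: "The differences between 3 groups were investigated using the repeated measures ANOVA followed by the Bonferroni post hoc tests". The chi-square and ANOVA tests also named there are for baseline comparability. The method serves four measures (range of motion, MAS, MTS and FMA), all called primary.

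The document defines no analysis population and no rule for missing visits. It mentions no imputation, mixed model, dropout allowance or continued follow-up of patients who withdraw.

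Arm size is not settled. The Participants section says "Totally, 42 patients will be recruited". The Design section speaks of two groups of 21 but then lists three arms. The arms hold 14 patients if the total of 42 is right; the total is 63 if 21 per arm is right.

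**The concern.** Repeated measures ANOVA in its usual form works on one row per patient with every visit filled in. A patient with one gap is removed from the whole analysis of that outcome, not just from the visit that was missed. Consider a patient who has all three treatment sessions, is examined before treatment, immediately after and at 1 month, and misses the 3-month visit. Three of four values are in hand and none is used.

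Two things are at stake. The first is precision: the immediate and 1-month comparisons lose patients who were actually measured at those visits, in a trial with 14 or 21 per arm. The second is who is being compared: the early results become results for patients who later attended everything, a selection made after randomisation. If that selection is related to response, and differs by arm, the early contrasts can shift.

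**Working it through.** The plan has no power, effect size, SD or dropout figure, so there is nothing of its own to reproduce. Loss rates and correlations below are assumptions; four visits and 14 or 21 per arm come from the document.

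**1. The mechanism.** A within-patient repeated measures ANOVA was run on 42 simulated patients with four visits: 42 × 4 = 168 values, error df (42 − 1)(4 − 1) = 123. With one 3-month value removed (167 values) the routine refused to run because the data were unbalanced. It ran only after that patient's other three values were removed too: 164 values, error df (41 − 1)(4 − 1) = 120. This was not run in SPSS, but it shows the complete-row requirement of the method.

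**2. Collected values discarded if loss occurs only at 3 months.** Patients lost × 3 earlier values:

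| Assumed loss | 42 patients | 63 patients |
|---|---|---|
| 10% | 4.2 × 3 = 12.6 | 6.3 × 3 = 18.9 |
| 20% | 8.4 × 3 = 25.2 | 12.6 × 3 = 37.8 |

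**3. Variance at the immediate and 1-month visits.** Take the difference between two arms in mean change from baseline. With random loss d only at 3 months, a model using all visits has n patients per arm at the early visits; the complete-row analysis has n(1 − d). The variance ratio is about 1/(1 − d):

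- d = 0.10: 1/0.90 = 1.11
- d = 0.20: 1/0.80 = 1.25

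Simulation of two arms, at 21 and at 14 per arm, with exchangeable correlation 0.6 or 0.8 or AR(1) 0.8, gave about 9-13% and 25-30% extra variance. The excess over the formula arises because the number lost varies between trials.

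**4. Variance at 3 months.** The missed value is gone under any method, so the gain is smaller: the model recovers only what earlier visits predict. Let s be the variance of the 3-month value given the three earlier ones, divided by the variance of the change from baseline. The ratio is approximately [1/(1 − d)] / [s/(1 − d) + 1 − s].

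- Exchangeable 0.6: s = (1 − 3 × 0.36/2.2) / (2 × 0.4) = 0.509/0.8 = 0.636. Ratio at d = 0.10: 1.111/(0.707 + 0.364) = 1.04; at d = 0.20: 1.25/(0.795 + 0.364) = 1.08.
- AR(1) 0.8: s = (1 − 0.64) / [2 × (1 − 0.512)] = 0.36/0.976 = 0.369. Ratio at d = 0.10: 1.111/(0.410 + 0.631) = 1.07; at d = 0.20: 1.25/(0.461 + 0.631) = 1.14.

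The simulated range is about 2-7% at 10% loss and 5-17% at 20%. The lower ends fall below the formula because the prediction must itself be estimated from few patients.

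**5. Bias.** Loss at 3 months was made to depend on the 1-month score through a logistic model, with a true effect of 0.50 SD. At roughly 25% loss in control and 17% in active, the complete-row 1-month effect was about 0.47-0.49. With a weaker dependence (slope 0.5, 25% control loss) it was 0.493-0.496. For scale, the standard error of a difference in mean change with complete data is √[4(1 − ρ)/n]:

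- 21 per arm: √(1.6/21) = 0.28 at ρ = 0.6; √(0.8/21) = 0.20 at ρ = 0.8
- 14 per arm: √(1.6/14) = 0.34 and √(0.8/14) = 0.24

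The bias is about a tenth of a standard error or less in most of these settings.

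**The case against.** **The deletion is not written in the plan.** This stands. The document names a method and a package, not a procedure or data layout, and does not say in so many words that all four visits enter one model. A reader might infer that the plan states that incomplete patients are excluded; it does not. The exclusion is a property of the conventional form of the named method. But no subset of visits and no other procedure is mentioned, so four visits in one ANOVA is the natural reading. If a mixed model is already intended, one sentence would settle the matter.

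**Attendance may be good.** It may; the document gives no rate, and with no missed visits there is no loss. In arms this small, though, one absent patient is 1/21 = 5% or 1/14 = 7% of an arm.

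**A tempting larger figure.** If visits were missed independently at 5% or 10% at each of three follow-ups, 1 − 0.95³ = 14% or 1 − 0.90³ = 27% of patients would be incomplete. These should not be read as the size of the harm. They describe scattered misses, not late withdrawal, and they count patients removed, not information that a better method would recover.

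**The mixed model has its own assumptions.** Also true. It is unbiased in the simulation because loss was generated from an observed score, which is missing at random by construction. It does not protect against loss that depends on unobserved values. It also treats the recoded MAS grade as a number, but so does the planned ANOVA.

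**Conclusion.** The point holds as a weakness in the choice of method, and it should be corrected. The document specifies one outcome analysis, the usual form of that analysis discards partly followed patients outcome by outcome, and no other text keeps them.

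The main cost is precision at the two earlier follow-up visits, and it arises even when loss is purely random. The cost at 3 months is smaller. The sizes rest on assumed loss of 10% or 20% confined to 3 months and on assumed correlations of 0.6-0.8; in percentage terms they are much the same at 14 or 21 per arm.

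A reader might go further and infer that the early treatment comparisons would be seriously biased, or that sham patients would leave more often. The documents do not support either: they say nothing about who might leave, and in the settings tried the bias was about 0.01-0.03 SD, small beside a standard error of 0.20-0.34 SD and dependent on the mechanism assumed.

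**What to change.** Replace the repeated measures ANOVA with a linear mixed model for repeated measures (MIXED in SPSS):

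- Fixed effects for group, visit and group-by-visit.
- All randomised patients in their assigned group, with every available visit.
- Unstructured within-patient covariance, with a simpler structure named in advance in case it does not converge, and a small-sample degrees-of-freedom method where available.
- The Bonferroni adjustment kept for pairwise group comparisons, with a statement of the visit or visits at which they are made and that the adjustment covers them. The present text does not say this.
- A sentence that patients who miss a visit are still invited to later ones, and that missing visits are reported by arm.

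The number of arms and the number of patients per arm must be reconciled in any case, because the per-arm counts depend on them.

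The cost is about one paragraph of analysis wording. The downside is a few more covariance parameters in a small sample and reliance on missing at random. The software, data, patients, visits and staff stay the same.

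### Bonferroni post hoc tests are valid but needlessly conservative for the three arm comparisons: Holm's step-down holds the same 5% familywise error and, over the same comparisons, never rejects less

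*Combined protocol and SAP*

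**What the plan says.** The Statistical analysis section of the combined protocol and SAP states that "The differences between 3 groups were investigated using the repeated measures ANOVA followed by the Bonferroni post hoc tests", with significance set at 0.05. It does not say:

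- whether the pairwise tests depend on a significant F test;
- which F test counts (group, or group by time);
- whether Bonferroni covers the three arm pairs only, or pairs across visits.

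The Design section names three arms: "the radial shockwave therapy group (RSWT group), the botulinum toxin injection group, and the control group". The same sentence speaks of two groups of 21, and the Participants section says "Totally, 42 patients will be recruited". Under Outcome measures, "The evaluation will be done before therapy sections, immediately, 1 month after, and 3 months after 3rd section of therapy". That makes four assessments, three of them after treatment. Several measures share the label of primary outcome. No effect size, SD, target power or sample size derivation is given.

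**The concern.** Three arms give three pairs: shockwave versus control, toxin versus control, and shockwave versus toxin. These comparisons are the trial's answer. Bonferroni holds every pair to 0.05/3 = 0.0167, even after another pair has already been declared different. The 5% familywise guarantee does not need that. With about 42 patients, a real but moderate difference would more often be reported as not significant than the plan's own error rate requires, and the remedy needs no extra patients.

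**Working it through.** **Inputs from the documents.** Alpha 0.05, taken as two-sided because sidedness is not stated. Three named arms. Total 42, which is 42/3 = 14 per arm; 21 per arm in three arms would need 3 × 21 = 63. Both sizes are shown. The plan states no power, so there is no figure of its own to reproduce.

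**Assumptions.** One outcome, one three-arm contrast, normal data, SD 1, pooled error, no dropout. Shockwave and toxin are better than control by (1.0, 1.0) SD or by (0.8, 1.2) SD. Each setting was simulated at least 100,000 times.

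**Rules compared.**

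- Bonferroni: each pair at 0.05/3 = 0.0167.
- Holm: order the P values; test the smallest at 0.05/3 = 0.0167, the next at 0.05/2 = 0.025 and the last at 0.05, stopping at the first failure. For m comparisons the i-th smallest is tested at 0.05/(m − i + 1). Every threshold is at least 0.05/m, so Holm never rejects less than Bonferroni over the same m.
- Closed test: overall three-group F at 5%, then each pair at 5%. If the three means are not all equal, at most one pair can be equal, so only one false rejection remains possible.

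**Power (%).**

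| Comparison | Effects (shockwave, toxin) | Per arm | Bonferroni | Holm | Closed |
|---|---|---|---|---|---|
| Shockwave v control | 1.0, 1.0 | 14 | 56 | 59–60 | 67 |
| Shockwave v control | 1.0, 1.0 | 21 | 78 | 81 | 86 |
| Shockwave v control | 0.8, 1.2 | 14 | 36 | 42 | 52 |
| Shockwave v control | 0.8, 1.2 | 21 | 55 | 63 | 72 |
| Toxin v control (largest difference) | 0.8, 1.2 | 14 | 74.7 | 75.7 | 78.9 |
| Toxin v control (largest difference) | 0.8, 1.2 | 21 | 91.9 | 92.4 | 93.8 |

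Holm therefore gains about 3 to 8 points for shockwave versus control (for example 42 − 36 = 6) and at most about 1 point for the largest difference (75.7 − 74.7 = 1.0; 92.4 − 91.9 = 0.5).

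**Does the F gate matter?** Hardly. With (1.0, 1.0) and 14 per arm, Bonferroni has about 56% power with or without it. Over a wider set of effects (largest difference 0.4 to 3.0 SD) the gate cost 0 to 0.4 points. The loss comes from the division by three.

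**Familywise error, one contrast.** With all arms equal it is about 4.4% for ungated Bonferroni and for Holm (their first step is the same), 4.2–4.3% for gated Bonferroni and 5.0% for the closed test. With the two active arms equal and both 1.0 SD better than control, it is 1.7% for Bonferroni, 3.1% (14 per arm) or 3.7% (21 per arm) for Holm, and about 5% for the closed test. All hold 5%.

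**Pairs tested at the three post-treatment visits.** Four-visit simulation, assumed within-patient correlation 0.6, one F gate, one arm shifted by 2.5 SD:

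| Level per pair after the gate | One arm shifted at all visits | One arm shifted at one visit only |
|---|---|---|
| 0.05 | about 12% | 15–23% |
| 0.05/3 | about 4% | 6–9% |
| 0.05/9 | about 1.5% | 2–3% |

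The argument behind the closed test does not carry over to this case. Even 0.05/3 can exceed 5%. The family has to be stated.

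**The case against.** The strongest reply is that Bonferroni after ANOVA is a standard, valid choice, and that a more powerful method does not make the plan wrong. That stands: this is an improvement, not the correction of an error. It is also true that Bonferroni buys a lower error rate when one pair is truly equal (1.7%, against 3.1–3.7% with Holm), though the plan asks only for 5%.

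A reader might infer that the plan corrects twice for the same comparisons. The text does not support this. It gives an order of analysis and never makes the pairwise tests conditional on the F test; without that condition Bonferroni is the only correction, and with it the extra cost is negligible.

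A reader might also infer that Bonferroni brings no gain in error control and could simply be dropped after a significant F. That holds, against the 5% ceiling, only for one outcome and one three-arm contrast. The plan has four visits and names none as decisive, and unadjusted pairs at several visits could reach about 12–23%.

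Finally, the simulations compare three normal means at one time point, whereas the plan has repeated measures and an ordinal scale (MAS). The power figures are illustrative for that reason. Holm's error guarantee does not depend on that model, only on each pairwise P value being valid.

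**Conclusion.** The point holds as a cheap improvement. Holm keeps the 5% familywise guarantee under any reading of the analysis sentence and rejects at least as often as Bonferroni over the same family. In the assumed scenarios the gain for shockwave versus control is about 4 points (56% to about 60%) or 6 points (36% to about 42%) with 14 per arm, and about 1 point or less for the largest difference.

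No fixed loss of power can be attributed to this trial. The effect sizes are assumed. Even for the more powerful closed test, the advantage over gated Bonferroni ran from 0 to 17.6 points across the effects examined. It is also unclear whether there are two groups of 21 or three arms, and 42 or 63 patients; that must be settled first. Neither Bonferroni over arm pairs nor Holm over arm pairs adjusts across the several primary outcomes, which is a separate matter.

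**What to change.** In the analysis sentence, replace the reference to Bonferroni post hoc tests with: *pairwise comparisons with Holm-adjusted P values over all comparisons in the family (three arm pairs, or three pairs times the visits tested).* State which of these families applies, which effect is tested (group, or group by time), and whether a significant F is required first.

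Only if one outcome and one contrast (a single visit, or the average over visits) is named as decisive may the closed test be used instead: overall three-group F at 5%, then each pair at 5%. In the two 14-per-arm scenarios it gives 67% and about 52% for shockwave versus control, at about 5% familywise error. It must not be applied to pairs at several visits.

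Cost: one or two sentences, and a hand adjustment of the unadjusted pairwise P values that SPSS prints. There are three downsides. Simultaneous confidence intervals no longer match the tests exactly, so ordinary 95% intervals would be reported beside them. Familywise error moves closer to 5%. And if 0.05/3 at each visit was intended, Holm over nine comparisons starts from a stricter 0.05/9 = 0.0056, which is the price of holding 5% over that larger family.
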